6.2.2 Early Study Termination/Suspension

If during the study it becomes evident to the Sponsor that the study should be stopped prematurely or placed on hold, appropriate notification will be given to the Investigator(s), IRBs, and FDA, as applicable. Bausch + Lomb will instruct the Investigators to stop/restart dispensing study materials and will arrange for study closeout, if applicable, at each site.

6.3 Subject Concomitant Medications/Therapy

Ocular medications or systemic or topical medications that, in the Investigator's opinion, could potentially affect ocular physiology or lens performance are prohibited, unless medically necessary during the course of the study.

6.4 Treatment Compliance

Treatment compliance will be assessed using lens wear parameter data.

6.5 Protocol Deviations

A deviation from the protocol is an unintended and/or unanticipated departure from the procedures and/or processes approved by the Sponsor and the IRB and agreed to by the Investigator. It is a Sponsor expectation that Investigators will follow the protocol and procedures as written. The Sponsor will not grant protocol waivers for this study. The Investigator may implement a deviation from the protocol to eliminate an immediate hazard to study subjects without prior IRB approval. As soon as possible after such an occurrence, the implemented deviation, as well as the reasons for it should be submitted to the IRB for review and approval. It should also be submitted to the Sponsor for agreement, and to the regulatory authorities, if required.

In the event a protocol deviation occurs, the date of and reason for deviations must be documented in all cases. Significant or major protocol deviations impacting the rights or safety of the subject, or the integrity of the study must be reported by the Investigator to the IRB and Medical Monitor immediately. Reporting of all other protocol deviations must adhere to the requirements of the governing IRB. Unless the protocol deviations put the subject at risk or the subject's condition requires that they be discontinued from the study, subjects may continue to participate until the end of the study.

Site Corrective Action Plans will be developed and completed as deemed necessary by the Sponsor, Sponsor designee (e.g., CRO) for sites or Investigators who deviate from this protocol in a way that adversely affects the rights, safety, or well-being of the subject(s) and/or the quality or integrity of data. The Site Corrective Action Plan will outline the deviation and the site's corrective and/or remedial actions. Decisions regarding critical deviations that merit Investigator disqualification and site closure will be made by the Sponsor and documented in the Trial Master File.

6. ADVERSE EVENTS

7.1 Introduction to Adverse Event Definitions

Adverse events, serious AEs (SAEs), significant non-serious AEs, non-significant non-serious AEs, adverse device effects (ADEs), anticipated serious adverse device effects (ASADEs), and unanticipated adverse device effects (UADEs) are defined in this section and in the protocol's glossary.

An AE is any untoward medical occurrence, unintended disease or injury, or untoward clinical signs (including abnormal laboratory findings) in subjects, users, or other persons, whether or not related to the investigational medical device, comparator, or the procedures involved. For users or other persons, this definition is restricted to events not related to investigational medical devices.

7.1.1 Serious Adverse Event (SAE) Definitions

An AE that (related or not related to the investigational test articles, comparator products or study procedures):

- Led to death.

- Led to serious deterioration in the health of the subject, that resulted in:
 - A life-threatening illness or injury; or
 - A permanent impairment of a body structure or a body function (e.g., blindness); or
 - Inpatient or prolonged hospitalization; or
 - Medical or surgical intervention to prevent life-threatening illness or injury or permanent impairment to a body structure or a body function.
- Led to fetal distress, fetal death, or a congenital abnormality or birth defect.

NOTE: A planned hospitalization for a pre-existing condition, or a procedure required by the protocol, without serious deterioration in health, is not considered an SAE.

Serious adverse events may include but are not limited to any hazardous, sight-threatening conditions occurring after exposure to the investigational test article including, but not limited to, the following:

- A presumed infectious ulcer (defined as a progressive erosion of the corneal tissue). For the purposes of reporting, this includes:
 - Central or para-central location
 - Penetration of Bowman's membrane
 - Infiltrate ≥ 2 mm diameter
 - Associated with iritis
 - Associated with any increase in intraocular pressure
 - Culture positive for microorganisms
 - Increasing size or severity at subsequent visits

NOTE: Signs of a presumed infectious corneal ulcer may include irregular focal infiltrates, active lesions with raised edges, significant diffuse infiltration, anterior corneal to mid-stromal involvement, erosion with overlying staining, conjunctival and lid edema, anterior chamber reaction (iritis), and severe bulbar and limbal redness. Symptoms associated with a presumed infectious ulcer (microbial keratitis) may include pain of rapid onset, severe redness, purulent or mucopurulent discharge, tearing, and photophobia.

- Any central or paracentral (within the central 6mm of cornea) corneal event that results in permanent opacification (such as corneal scar or vascularization)
- Any serious adverse ophthalmic events including hypopyon and/or hyphema
- Any neovascularization within the central 6mm of the cornea
- Permanent loss of ≥ 2 lines of BSCVA
- All cases of iritis

7.1.2 Significant Non-Serious Adverse Event Definitions

A significant non-serious adverse event is an AE that does not meet the serious criteria, is considered significant by the Sponsor, and requires expedited reporting to the Sponsor (see [Section 7.3.1](#)). These events include but are not limited to:

- Peripheral non-progressive non-infectious corneal ulcers
- All symptomatic corneal infiltrative events
- All cases of corneal staining greater than or equal to Grade 3
- A temporary loss of two or more lines of BSCVA (for greater than or equal to 2 weeks)
- Neovascularization cases Grade 2 or greater (if not within the central 6mm of the cornea)
- Any ocular event that necessitates temporary lens discontinuation of greater than or equal to 2 weeks

7.1.3 Non-Significant Non-Serious Adverse Events Definitions

A non-significant non-serious adverse event may include but is not limited to the following and does not require expedited reporting:

- Bacterial conjunctivitis
- Viral conjunctivitis
- Allergic conjunctivitis
- Corneal edema
- Contact lens related papillary conjunctivitis
- Loss of contrast sensitivity

7.1.4 Adverse Device Effect (ADE) Definitions

An adverse device effect is an AE that is assessed to be related to the use of an investigational medical device. This definition includes AEs resulting from insufficient or inadequate instructions for use; deployment, implantation, installation, or operation; or any malfunction of the investigational medical device. This definition also includes any event resulting from use error or from intentional misuse of the investigational medical device.

7.1.4.1 Anticipated Serious Adverse Device Effect (ASADE) Definition

An anticipated serious adverse device effect (ASADE) is an ADE that first meets the serious criteria (see [Section 7.1.1](#)) and which, by its nature, incidence, severity, or outcome, has been previously identified in the investigational plan or application (including a supplementary plan or application) and/or in the risk analysis report. ASADEs include but are not limited to:

- Corneal ulcer (infectious or non-infectious)
- Keratitis

- Sensitivity to light (photophobia)
- Excessive eye secretions including mucopurulent discharge
- Blurred vision, rainbows, or halos around objects
- Poor visual acuity (reduced sharpness of vision)
- Moderate to severe eye pain not relieved by removing the lens

7.1.4.2 Unanticipated Serious Adverse Device Effect (USADE) Definitions

An unanticipated serious ocular or non-ocular adverse device effect is an adverse event related to the use of an investigational medical device that has resulted in any of the consequences characteristic of a serious adverse event as described in [Section 7.1.1](#) and which by its nature, incidence, severity or outcome has not been identified in the current version of the risk analysis report.

This definition includes but is not limited to AEs resulting from insufficient or inadequate instructions for use, deployment, or any malfunction of the investigational medical device.

This definition also includes any event resulting from use error or from intentional misuse of the investigational medical device. USADEs include but are not limited to

- Any central or paracentral (within 6 mm of cornea) corneal event that results in permanent opacification (such as corneal scar or vascularization)
- Any serious adverse ophthalmic events including hypopyon and/or hyphema
- Any neovascularization within the central 6 mm of the cornea
- Permanent loss of ≥ 2 lines of BSCVA
- All cases of iritis.

7.1.5 Relationship Definition: Study Device and/or Other Study Materials

- **Related:** There is at least a reasonable possibility that the AE is related to the study device and/or rewetting drops. Reasonable possibility means that there is evidence to suggest a causal relationship or association between the study device and/or rewetting drops and the AE.
- **Not related:** There is little or no reasonable possibility that the AE is related to the study device and/or rewetting drops. This assessment implies that the AE has no evidence to suggest either a causal relationship or association to the study device and/or Rewetting Drops and a more likely or certain alternative etiology exists.

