3.1 Description of Study Design

This is a single-treatment study evaluating the safety and effectiveness of the Arise Orthokeratology Lens with non-spherical posterior peripheral curves.

Approximately 90 subjects (180 eyes) will be enrolled in this 3-month, multi-center, single-arm, open-label study at approximately 6-10 investigative sites in the United States (US).

All subjects will be seen for a Screening Visit at which informed consent will be obtained and eligibility assessed. If subjects satisfy all eligibility criteria, they will be enrolled in the study. Subjects will be seen to assess the treatment effect of overnight orthokeratology over a 3-month period. All subjects will be assigned a subject identification (ID) number in sequential order by the Electronic Data Capture (EDC) system. At the Screening Visit, if a subject is eligible, study lenses will be ordered specifically for that subject. Eligible subjects will come back approximately 2 weeks after the Screening Visit for a Dispensing Visit. Each subject will also be dispensed Boston SIMPLUS Multi-Action Solution, including a study lens case, and Boston Rewetting Drops. These solutions will be replenished during the study as needed. Subjects must NOT use ANY other cleaning and disinfecting solution or rewetting drops during the study unless the Investigator transitions individual subjects to a different Boston Lens Care System. Subjects will be required to wear their study lenses for a minimum of eight (8) hours on an overnight wear basis for approximately 3 months, with scheduled in-office follow-up visits at 1-day, 1-week, 1-month, 2-months and 3-months. These follow-up visits must be conducted within 2 hours of the subject removing the study lenses.

Daily disposable soft contact lenses (Bausch + Lomb Biotrue ® ONEday (nesofilcon A) Contact Lenses known as “maintenance lenses”) will be dispensed to provide supplemental visual correction during the day as needed for the orthokeratology lens adaptation period.

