3. STUDY MATERIALS

Bausch + Lomb will provide the Investigator all orthokeratology contact lenses, anesthetic drops and lens care products required for the study.

The following care system for study lenses will be provided prior to the start of study:

- Boston SIMPLUS® Multi-Action Solution for cleansing, rinsing, disinfecting, and storing the lenses.
- Boston® Rewetting Drops for rewetting lenses.
- NOTE: Investigators have the option of dispensing any Boston Lens Care System if, in their judgement, Boston SIMPLUS is not the preferred regimen (e.g., not the subject's habitual Boston Lens Care System, or is not performing satisfactorily).

Although the majority of subjects may not require maintenance lenses, Bausch + Lomb will provide each investigative site a supply of Bausch + Lomb Biotrue® ONEday (nesofilcon A) Contact Lenses in representative powers of -0.50, -1.00, -1.50, -2.00, -2.50, and -3.00D for use as needed during the orthokeratology lens adaptation phase.

Use of habitual soft contact lenses and lens care products other than those provided for this study is not allowed during the study period.

Conformity to general safety and performance requirements to protect the health and safety of the subjects for the investigational test article are addressed in the design verification-design review process referenced in [BL SOP 20-D022-3, Investigational Material Release for Bausch Health Companies R&D Activities](#).³

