4.1 Description of Test Article (Test)

The Test lens to be used in this study is the Arise Orthokeratology (oprifoccon A) Lens. The Arise Orthokeratology Lens is a lathe cut contact lens with a spherical or aspherical

base curve and non-spherical posterior peripheral curves. The posterior curve is selected to properly fit an individual eye for orthokeratology and the anterior curve is selected to provide the necessary optical power for a temporary reduction of myopia. A peripheral curve system on the posterior surface allows tear exchange between the lens and the cornea. The Arise Orthokeratology Lens is manufactured by Bausch & Lomb Incorporated, Lancaster, NY and shipped in Boston SIMPLUS Multi-Action Solution.

A Fitting Guide for Arise Orthokeratology Lens is provided in Appendix D: Fitting Guide.

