8.6.2 Adverse Events

All AEs occurring during the study will be recorded and classified on the basis of MedDRA terminology. Descriptions of AEs will include the date of onset, the date the AE ended, the severity of the AE, the relationship to the study device, the action taken to treat the AE, and the outcome. All reported treatment—emergent AEs (TEAEs) will be summarized by the number of subjects (or eyes, as appropriate) reporting AEs, system organ class, severity, seriousness, and relationship to study device. TEAEs are those AEs with onset on or after the date of the first study device use.

Serious adverse events will be summarized at the subject and eye levels.

Adverse events will be summarized by severity. Each subject (or eye, as appropriate) will be counted only once within a system organ class or a preferred term by using the AEs with the highest severity within each category.

Adverse events will be summarized by relationship to study device. Each subject (or eye, as appropriate) will be counted only once within a system organ class or a preferred term by using the AEs with the greatest relationship within each category.

All information pertaining to AEs noted during the study will be listed by subject, detailing verbatim given by the Investigator, preferred term, system organ class, start

date, stop date, severity, action taken, and device relatedness. The AE onset will also be shown relative (in number of days) to the day of initial use of the study device.

Serious adverse events (SAEs) will be tabulated.

In addition, a list of subjects who discontinued from the study and a list of subjects who experienced SAEs will also be provided.

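### The relatedness definition in Section 7.1.5 covers the lens and rewetting drops only, so the related-AE tables are neither device-only nor study-material-wide

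*Combined protocol and SAP*

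**What the plan says.** Section 7.1.5 is headed "Relationship Definition: Study Device and/or Other Study Materials". It has two categories. *Related* is defined by "There is at least a reasonable possibility that the AE is related to the study device and/or rewetting drops", and evidence of either a causal relationship or an association is enough. *Not related* is defined by "There is little or no reasonable possibility that the AE is related to the study device and/or rewetting drops", and adds that "a more likely or certain alternative etiology exists". Both name the same two items, and there is no third category.

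The device is identified in Section 4.1: "The Test lens to be used in this study is the Arise Orthokeratology (oprifoccon A) Lens". Subjects meet several other sponsor-supplied products. Section 3.1 states: "Each subject will also be dispensed Boston SIMPLUS Multi-Action Solution, including a study lens case, and Boston Rewetting Drops". The same section provides for daily disposable soft maintenance lenses as needed during adaptation. The Study Materials chapter adds: "Bausch + Lomb will provide the Investigator all orthokeratology contact lenses, anesthetic drops and lens care products required for the study". Section 6.1.2 has an anesthetic drop put in each eye before the lens is placed at Dispensing.

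Section 7.2 tells the investigator to judge whether an event is related to the study device and refers to Section 7.1.5 for how. Section 8.6.2 then states: "Adverse events will be summarized by relationship to study device". Its AE listing includes device relatedness.

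**The concern.** The heading and the text of Section 7.1.5 do not agree, and later sections attach a third meaning. The heading covers all study materials, the text covers the lens plus one ancillary product, and Sections 7.2 and 8.6.2 describe the result as relationship to the device.

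In a single-arm study with no comparator, investigator attribution is one of the few ways to separate events due to the lens from background events and from events due to the products used with it. If the *Related* column holds drop reactions but not solution, maintenance-lens or anesthetic reactions, it answers neither of the two questions a reader would ask: how many events were attributed to the lens, and how many to anything the study supplied.

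**Working it through.** No arithmetic applies, and the plan gives no figure to reproduce. The check sets the definition against each supplied product and follows an AE attributed to that product *alone* through to the table.

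| Item to which the AE is attributed | Where it enters the study | Named in 7.1.5? | Code under 7.1.5 | Place in the 8.6.2 relationship table |
|---|---|---|---|---|
| Arise lens | 4.1 | Yes | Related | Device-related, correctly |
| Rewetting drops | 3.1, Study Materials | Yes | Related | Device-related, though the drops are not the device |
| Lens care solution | 3.1, 6.1.2, Appendix C | No | Could be Not related | Could be shown as unrelated |
| Maintenance lens | 3.1, Study Materials | No | Could be Not related | Could be shown as unrelated |
| Anesthetic drop | Study Materials, 6.1.2 | No | Could be Not related | Could be shown as unrelated |

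**Why the last three rows can fall under *Not related*.** That category needs (i) little or no reasonable possibility of a link to the lens or the rewetting drops and (ii) a more likely alternative cause. If the investigator judges that the solution, the maintenance lens or the anesthetic caused the event, that product is itself the alternative cause in (ii). With only two categories, nothing else is available.

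**Do later sections repair it?** No.
- Section 7.2 asks about the study device alone and sends the investigator to Section 7.1.5, where the drops count as well.
- Section 8.6.2 has no row for other materials. It counts each subject or eye once per term at the greatest relationship, so a single drop-only event puts that subject or eye in the related column for that term.
- An anesthetic reaction at Dispensing is not screened out as pre-treatment. Section 8.6.2 calls an AE treatment-emergent if its onset is on or after the date of first device use, and the lens is first placed on the eye at that visit.
- No readable section gives separate causality categories for the solution, maintenance lenses or anesthetic.

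**What does not depend on relatedness.**
- The primary safety outcome is the rate of all serious AEs (Section 8.1.1).
- SAEs go to the sponsor within 24 hours whatever their relationship (Section 7.3.1).
- Significant non-serious AEs are defined without reference to cause (Section 7.1.2).
- The AE definition in Section 7.1 applies to related and unrelated events alike.

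**The case against.** The strongest reply is that the care solution reaches the eye on the study lens. Lenses are shipped in Boston SIMPLUS, soaked in it for at least 4 hours, rubbed and rinsed with it, and then inserted. Since evidence of an association with the lens is enough for *Related*, an investigator could reasonably code a solution reaction that way. This stands, and it is why the point says *could be coded*, not *would be coded*. It still leaves the coding to individual judgement across the planned 6 to 10 sites, and it does not help with maintenance lenses or the anesthetic, which do not arrive on the study lens.

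A second reply is that the objective concerns the Arise lens, so attribution centered on the device is defensible. That is fair, but the present definition is not device-only either, because it includes the drops. The reply does rule out one remedy: merging every product into a single *Related* category would dilute the device signal.

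Third, the AE eCRF is not in the documents and may already separate lens from drops. That is possible. Section 8.6.2 nevertheless plans only one relationship summary.

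A reader might also infer that a serious solution-related event would escape the IRB report for unanticipated serious device effects because of Section 7.1.5. The documents do not support this. Sections 7.1.4 and 7.1.4.2 limit ADEs and USADEs to events related to the investigational device, so an event due purely to the solution is outside them whatever Section 7.1.5 says, and rewording Section 7.1.5 would not bring it in.

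**Conclusion.** The inconsistency is real. Followed literally, Section 7.1.5 counts drop-only events as device-related and allows events due only to the solution, maintenance lens or anesthetic to be coded *Not related*. The related-AE tables are therefore neither device-only nor study-material-wide.

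The size cannot be estimated. All subjects use a Boston care solution, but that is exposure and must not be read as a misclassification rate. The other two exposures are smaller: the Study Materials chapter expects that most subjects may not need maintenance lenses, and the anesthetic is scheduled only at Dispensing. The effect is limited to causality coding and the Section 8.6.2 tables and listings. The primary SAE rate and SAE reporting are untouched, so this is a minor correction.

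The conclusion assumes that investigators apply Section 7.1.5 as written and that no blacked-out text or unseen eCRF instruction separates causality by product.

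**What to change.** In Section 7.1.5, ask for two separate judgements: relationship to (a) the study lens, and (b) other study materials, listed as rewetting drops, lens care solution, maintenance lenses and anesthetic drops. Reword the Section 7.2 prompt to match. Record the implicated item on the AE eCRF. In Section 8.6.2, tabulate device-related AEs and any-study-material-related AEs separately, and show the item in the listing. The separation is essential, because it keeps the lens signal undiluted.

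The cost is protocol wording, one more eCRF field and one more table. The count of AEs related to any study material will be slightly higher than the present *Related* count, while drop-only events will leave the device-related count. No visit, assessment, subject number or primary outcome changes.
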